16.2 Recruitment period and study duration

The recruitment period is scheduled to start in March 2018 and will last 12 months. The primary endpoint (feasibility) will be reached maximum 6 months after inclusion of the last patient. Documentation and data evaluation will take about 3 months. The primary result of the study will probably be available in end 2019.

16.3 Analysis

Patient and tumor characteristics are given as absolute and relative frequencies. Doses, volumes, fractions are listed by technique, by localization of metastasis, and by size. Maximum and median doses applied to organs at risk are described as median, inter-quartile range, and maximum. Summary compliance measures use the worst observation. Further parameter estimation, confidence intervals and tests using data at the metastasis level account for correlation by using GEE methods.

Toxicities are tabulated by grade and time and shown as time profiles of cumulated grades. Adverse events are listed by system organ class (MedDRA), intensity and causality. Progression free survival is estimated using the Kaplan-Meier method.

17 Early termination

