Exclusion criteria (recruitment is not possible if any -at least one- criterion is met)	
 • Relevant comorbidity (with limitations to administer radiotherapy according to protocol) • Prior radiotherapy which results in limitations to administer radiotherapy according to protocol • No large metal implants in vicinity of lesion • Department dose constraints for normal tissue can't be met • Large bony lesions with extensive osseous destruction • Patients symptoms do not correlate with MR findings
Study therapy	
 • Image guided radiotherapy (IGRT) with hypo-fractionated simultaneous integrated boost (IMRT) • GTV1 = MR T2w lesion and ADC $\leq 1200 * 10^{-3}$ mm2/s • GTV2 = MR T2w lesion and ADC \leq median ADC in GTV1 • Each lesion is a CTV, CTV = GTV • PTV=CTV+ margin according to department standards • Dose-fractionation • CTV1: 4 x 5 Gy • CTV2: 4 x 7 Gy
Primary endpoint	Feasibility: Proportion of study participants that complete radiotherapy with $\geq 90\%$ of prescribed dose
Secondary endpoints	
 • Dominant symptom (VAS) • Progression-free survival >6 months • Overall survival

	
• Acute toxicity• Quality of life• Change in ADC from before to end of treatment• Change in ADC from before to 6 month post treatment
Sample size	34 patients has to be included in the study
Study sites	University Hospital Sjaelland, Naestved UKSH Campus Kiel UKSH Campus Luebeck
Time table	Recruitment period: 12 months Start of study: March 2018 End of study: March 2019 Follow-up: minimum \geq 6 months
Financing	Interreg (InnoCan)

3 Background and rationale

Prostate cancer is the major cause of cancer death in men living in developed countries. Large autopsy studies found that patients that presented prostate cancer demonstrated metastatic disease in 35% of cases. Prostate cancer metastases were 90% bone metastases, with 90% of the bone metastases involved the spinal cord, followed by lung (46%), liver (25%) and pleura (21%). Another important pathway is the lymphatic system, which is involved in 9 to 16% of cases, especially at the level of obturator, pre-sacral, internal, and common iliac arteries, and sometimes even the extra-regional para-aortic chains (1).

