10.3 Target volumes

Patients included in the study will be subjected to a protocol-specific MRI examination (see MR sequence and example of target delineation in appendix 19-20). A radiologist will read the MRI scan to validate correspondence between MR lesion and the patients dominating symptoms. In case of more than one lesion, decision on priority of target volumes will be made by the radiation oncologist based on clinical expertise. An ADC map will be calculated for the lesion using the DWI sequences. A cutoff ADC value of less than 1200×10^{-6} mm²/s in combination with a T2w image will be used to predict the MR lesion (GTV1) (26). The most aggressive part of the lesion (GTV2) will be defined using ADC of less than or equal to a cutoff value calculated as the median ADC value for the GTV1 (25). Notice that GTV2 need not to be one coherent volume, but may consist of several sub-volumes.

For the definition of target volumes, the following aspects should be considered: The clinical target volume (CTV) is the visible macroscopic tumor (GTV). The safety margin for the planning target volume (PTV) should be according to the department standard, and depending on the radiation technique used. The margin for the PTV2 for CTV2 may be chosen to be smaller than for PTV1 as this volume is enclosed in the CTV1, which receives a dose of 4 x 5Gy already.. For the treatment of breathing-dependent lesions (upper abdomen), treatment techniques with motion compensation (e.g. breath-hold or gating) should be used. All four fractions of the treatment should be given within two weeks of starting the radiotherapy.

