16.1 Case number

The objective of this study is to investigate the feasibility of applying hypo-fractionated radiotherapy to treat a dominant symptomatic lesion in patients with HRPC. The hypothesis is that at least 90% of the recruited patients complete combined systemic and local treatment with at least 90% of scheduled radiation dose administered. We use a two-sided one-sample proportion score test to compare the proportion of feasible cases to a reference value of 90%. We want to detect any difference with statistical significance of 5% and a power of 80% for not overlooking a true proportion non-feasible of 70%. The necessary sample size is estimated to 24 cases. Drop-out may happen either due to exclusion, or because patients withdraw their consent for participation. For patients with poor prognosis a realistic drop-out rate is estimated to be 30%, which implicated that **34 patients** must be included in the study to reach significance.

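### Section 16.3 names GEE for metastasis-level inference with only 24 to 34 patients as clusters and states no small-sample correction

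*Protocol*

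**What the plan says.** Section 16.3 of the protocol (Analysis) states that further estimates, confidence intervals and "tests using data at the metastasis level account for correlation by using GEE methods". It does not name the variance estimator, link, working correlation, reference distribution or any small-sample adjustment.

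The number of clusters follows from section 16.1 (Case number): "The necessary sample size is estimated to 24 cases". After allowance for drop-out, the synopsis gives "34 patients has to be included in the study".

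The number of lesions per patient is not stated. The design targets one dominant symptomatic lesion, but section 10.3 allows for several: "In case of more than one lesion, decision on priority of target volumes will be made by the radiation oncologist based on clinical expertise".

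Section 4 intends to relate patient characteristics, comorbidities and tumour factors to outcomes. Section 11.5 plans comparative volume and ADC statistics.

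**The concern.** The GEE sandwich variance is justified for a large number of independent clusters. With few clusters, the fitted residuals are systematically smaller than the true errors, so the variance is underestimated. A normal reference then ignores the uncertainty of that variance. What counts is the number of patients, and in a group comparison the number in the smaller group. The shortfall is therefore present even if every patient contributes one lesion.

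At stake are the lesion-level intervals and tests, for example on ADC and volume change by tumour factor. Section 4 says that the results may lead to a randomised dose-escalation study, so intervals that are too narrow could make a lesion-level signal look firmer than it is when that study is planned.

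**Working it through.** **1. The plan's own figures.** Section 16.1 specifies: "We use a two-sided one-sample proportion score test to compare the proportion of feasible cases to a reference value of 90"%, with "statistical significance of 5% and a power of 80"%. The alternative is worded "for not overlooking a true proportion non-feasible of 70"%. The stated number is reproduced when 70% is read as the feasible proportion:

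n = [(1.96·√(0.9·0.1) + 0.8416·√(0.7·0.3)) / (0.9 − 0.7)]² = [(0.5880 + 0.3857)/0.2]² = 23.70, rounded up to 24.

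On drop-out the protocol says "For patients with poor prognosis a realistic drop-out rate is estimated to be 30"%: 24/0.70 = 34.3, stated as 34. The cluster count is therefore 24 to 34. This calculation is at patient level and does not involve GEE.

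**2. Size of the bias in the simplest case.** Assume one lesion per patient, a continuous outcome and equal variance. In a group of n patients, the uncorrected sandwich has expectation (n − 1)/n times the true variance of the group mean. For a contrast of a versus b patients:

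ratio = [(a−1)/a² + (b−1)/b²] / [1/a + 1/b]

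- Single mean, 24 patients: 23/24 = 0.96.
- 12 v 12: 11/12 = 0.92.
- 6 v 18: (0.1389 + 0.0525)/0.2222 = 0.86.
- 3 v 21: (0.2222 + 0.0454)/0.3810 = 0.70.
- 4 v 30: (0.1875 + 0.0322)/0.2833 = 0.78.

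**3. Coverage by simulation.** Same setting, no true difference, nominal 95%. The corrected column uses K/(K−1) with t(K−1) for a mean, and Mancl-DeRouen with t(K−2) for a contrast, where K is the number of patients.

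| Patients | Estimate | Uncorrected, z | Corrected, t |
|---|---|---|---|
| 24 | mean | 93% | 95% |
| 24 | 12 v 12 | 93% | 96% |
| 24 | 6 v 18 | 90% | 95% |
| 24 | 3 v 21 | 81% | 91% |
| 34 | mean | 94% | 95% |
| 34 | 17 v 17 | 93% | 96% |
| 34 | 8 v 26 | 91% | 95% |
| 34 | 4 v 30 | 85% | 92% |

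At 6 v 18 the type I error is about 100 − 90 = 10%, twice nominal. With 1–3 lesions per patient and intra-patient correlation 0.3, the results are similar.

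**4. Sensitivity to what the protocol does not give.** Further simulations used 24 or 34 patients, an independence working correlation and other lesion counts, with intra-patient correlation 0.5 (continuous) or 0.3 (binary).

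- *Continuous, skewed 1–10 lesions per patient:* a single mean covers 90.0% (24 patients) and 91.5% (34). Contrasts are lower, down to 85.0% at 6 v 18.
- *Continuous, 70/20/10% of patients with 1/2/3 lesions:* 6 v 18 covers 88.6%.
- *Continuous contrasts at 50:50 or 25:75, all lesion patterns:* 85.0–93.2% uncorrected, 93.6–96.0% corrected.
- *Binary, event proportion 0.5–0.9, uncorrected:* risk differences 83.1–97.1%. Odds ratios 88.6–99.9% in the samples where they can be estimated.

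**The case against.** The strongest objection is that the protocol says only that GEE methods are used. GEE with a bias-corrected variance and a t reference is also a GEE method. The choice of sandwich variant is often left to a statistical analysis plan, and that document is not at hand. This stands: a reader might infer that the protocol commits to uncorrected GEE, and it does not. What remains is that 16.3 already fixes the method in the protocol, the usual form of that method suits the protocol's own patient numbers poorly, and nothing in the text guards against it.

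A second objection is that no lesion-level comparison is planned, because section 16.3 merely lists doses, volumes and fractions by technique, localisation and size. This holds for that listing. But 16.3 announces metastasis-level tests, and section 4 plans to relate patient and tumour factors to outcomes. No particular split is announced, however, so a group of 3 or 4 patients is an assumption.

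A third objection is that undercoverage is not universal. This stands, as the binary results show. A single proportion near 0.95 on the identity scale can cover about 78%, but there the correction hardly helps (78.3% to 78.4% at 24 patients with mostly one lesion). The cause is the Wald interval near the boundary, not the number of clusters.

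Finally, the consequences are limited. The primary endpoint uses a patient-level score test, compliance summaries take the worst observation, and progression-free survival uses Kaplan-Meier. None of these depends on GEE.

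**Conclusion.** The point holds as a conditional one. If GEE is run with an uncorrected sandwich variance and a normal reference on 24 to 34 patients, nominal 95% intervals for continuous lesion-level outcomes cover about 90–94% for a single mean or for contrasts down to a 25/75 split. Coverage is about 81–85% when one group has 3–4 patients. The figures assume one or a few lesions per patient and modest intra-patient correlation. Strongly unequal lesion counts lower the contrasts further, to 85% at 6 v 18.

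Two stronger readings are not supported. One is that every lesion-level test rejects too often: some binary and odds-ratio settings are at or above nominal. The other is that a single coverage figure can be attached to this trial: lesion counts, correlations, event rates and splits are all absent from the protocol.

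The effect is confined to secondary lesion-level analyses. It is worth correcting because the remedy is a standard one and restores about 95% for continuous outcomes, except in the very small groups.

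**What to change.** Add one sentence to section 16.3. GEE analyses at metastasis level use a small-sample bias-corrected sandwich variance (for example Mancl-DeRouen) with a t reference on patients minus parameters degrees of freedom, and comparisons in which a group has fewer than about five patients are reported descriptively only. The second half is needed because, at 3 v 21 and 4 v 30, the correction reaches only 91–92%.

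The cost is a standard software option and slightly wider intervals. Some binary outcomes become slightly conservative: for a risk difference at event proportion 0.9, 12 v 12 and one lesion each, coverage goes from 93.6% to 98.6%. The correction does not repair Wald intervals for proportions close to 0 or 1. The sample size and the primary analysis stay as they are.

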The aim of the present study will be to conduct a feasibility study of a new short palliative radiotherapy regime that apply to patients with metastatic HRPC patients presenting with a dominating debilitating symptom and an expected reasonable survival. The dominant symptom can be such as pain, urinary retention, chronic rectal obstruction, bleeding etc., caused by localized progression of the patient's metastatic prostate cancer. This new approach will apply magnetic resonance imaging (MRI) to verify correspondence between the progressing HRPC lesion (DSL =the dominant symptomatic lesion) and the patients corresponding dominant symptom. Diffusion weighted MR imaging (DWI) will apply to identify both the lesion and the most aggressive part of the lesion. The symptomatic lesions will be treated using precision radiotherapy (IGRT+IMRT/VMAT or SBRT/SRS if available) with a dose of 4 x 5 Gy, while for the most aggressive part of the lesion the dose will be escalated to 4 x 7 Gy using a simultaneous integrated boost (SIB) technique.

4 Objective

This prospective study will evaluate the feasibility as the primary endpoint. Secondary endpoints are visual analog score (VAS) of the dominating symptom, symptom progression free survival, evaluation of radiation induced acute toxicity, the influence on quality of life, the progression free survival and change in volume and ADC statistics from baseline as surrogate marker of local response to radiotherapy. The study will analyze patient characteristics, relevant comorbidities and tumor related factors correlation to outcomes. Based on the results of this study, a prospective randomized phase II/III dose escalation study may suggested.

5 Study design and participating centers

This is an international, multi-center single arm prospective feasibility study. Participating sites are:

1. University Hospital Sjaelland, Naestved, Department of Oncology
2. UKSH Campus Kiel, Department of Radiation Oncology
3. UKSH Campus Luebeck, Department of Radiation Oncology

6 Inclusion and exclusion criteria

Patients can be included in the study if they fulfill all of the following inclusion criteria and none of the following exclusion criteria.

Inclusion criteria:

- Patients with hormone refractory biopsy proven prostate cancer (HRPC)
- Presenting with a dominating debilitating symptom
- Expected median survival of 3-12 months (6)
- Focal irradiation of lesion is feasible
- Systemic therapy according to guidelines

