10.1 General remarks

The primary endpoint is feasibility. The secondary endpoints are duration of relief from local symptoms, i.e. local symptom progression free survival (LPFS), overall survival, treatment toxicity (RTOG/CTCAE 4.0), Quality of life (EORTC-QLQ-C30 and EPIC26), and change in ADC as surrogate marker of response (21-25). Patients are scheduled for protocol specific follow-up visits at 1, 3, 6 months after end of radiotherapy. Additional MRI (T2w and DWI) will be performed at 1 and 6 months after end of radiotherapy or in case of progression of the dominant symptom.

Preferred technique is hypo-fractionated with high precision radiotherapy (radiosurgery or stereotactic radiotherapy) with few (1 to 5) fractions and ablative total dose. Daily IGRT is mandatory for hypo-fractionated regimens. For the treatment of thoracic lesions and metastases in the upper abdomen, techniques for motion compensation (e.g. breath-hold- or gating techniques) should be used, if available. In specific situations (e.g. spinal metastases with involvement of the spinal canal or cord compression or metastases with infiltration of hollow organs), however, lower doses of radiotherapy may be necessary for adherence of dose constraints or to avoid radiation-induced complications such as perforation. In these cases, moderately hypo-fractionated or even conventionally fractionated regimens should be used. The total dose should exceed at least a dose equivalent to 50Gy in conventional fractionation.

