12.1 Adverse events

An adverse event (AE) is defined as any event experienced by a patient or subject of a clinical trial, which does not necessarily have a causal relationship to the study treatment.

The severity of AEs should be assessed by using the National Cancer Institute Common Terminology Criteria for Adverse Events (CTCAE version 4.03). If an AE occurs, which is not described in the CTCAE version 4.03, the following five-point scale should be used for assessment: grade 1 = mild, grade 2 = moderate, grade 3 = severe, grade 4 = life-threatening and grade 5 = fatal.

The investigator must also systematically assess the causal relationship of the AEs to the trial treatment. The AEs should therefore be classified as reasonably related or not reasonably related (unrelated) to trial treatment.

- All AEs experienced will be documented in the appropriate section of the CRF.
- Any clinical AE with severity of grade 4 or 5 must also be reported as an SAE.

Severe adverse events (SAE)

A severe adverse event (SAE) is any untoward medical occurrence that meets the following criteria:

- Results in death.
- Is life-threatening
- Requires hospitalization or prolongs an existing hospitalization.
- Results in persistent or significant disability
- Is a congenital anomaly or birth defect.
- Is otherwise considered medically important.

All SAEs must be documented and reported to the sponsor within 24 hours after awareness of the event using the online web interface for Easytrial.

13 Data and Safety Monitoring Board

Data will be entered pseudonymously into an online web based electronic database, Easytrial, and data stored on servers in Denmark. Access to the web interface is by invitation via email to staff participating in the study only. The Data and Safety Monitoring Board (DSMB) reviews safety after the first ten and after the

last patient have been treated and the respective data validated and tabulated. It may recommend restrictions to treatment regimens and patient eligibility.

14 Endpoint Adjudication Committee

The Endpoint Adjudication Committee (EAC) receives pseudonymized MRI scans and the Radiotherapy treatment plan for all patients up to end of trial. The EAC will assess when progression free survival ended.

15 Quality Assurance

The Monitoring at the German sites according to GCP is performed by ZKS Kiel/Luebeck.

The Danish sites will be monitored according to the Danish regulations in their own responsibility.

16 Statistical aspects

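### The progression endpoint is named in conflicting ways and gives death no role, so the single Kaplan-Meier curve cannot be read as duration of symptom relief

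*Protocol*

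**What the plan says.** The Protocol describes the progression endpoint in six places, and they do not agree.

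- Synopsis, secondary endpoints: "Progression-free survival >6 months", a six-month landmark with no event defined.
- Section 4: two separate items in one list, "symptom progression free survival, evaluation of radiation induced acute toxicity, the influence on quality of life, the progression free survival".
- Section 10.1: "The secondary endpoints are duration of relief from local symptoms, i.e. local symptom progression free survival (LPFS), overall survival". Only the local symptom version appears, and it is equated with a duration of relief.
- Section 14: "The Endpoint Adjudication Committee (EAC) receives pseudonymized MRI scans and the Radiotherapy treatment plan for all patients up to end of trial". The committee then decides when PFS ended, with no local or symptom qualifier. The VAS is not in the listed material.
- Section 16.3: "Progression free survival is estimated using the Kaplan-Meier method". This is the only analysis stated for any progression endpoint.
- Appendix 4 flowchart: LPFS is recorded after radiotherapy and at 1, 3 and 6 months. VAS and survival are recorded at the same visits.

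Eligibility (Section 6) requires an expected median survival of 3 to 12 months.

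**The concern.** A reader cannot tell whether the event is worsening of the dominant symptom, local progression on MRI or any disease progression, nor what happens to a patient who dies first. The endpoint in 10.1 is symptom-based, while the one adjudicated and analysed is PFS without qualifier, so the symptom endpoint has no matching analysis.

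Death cannot be treated as a detail in this population. If it counts as an event, a patient who dies with the symptom still relieved is scored as a failure. If it is censored, the curve describes a setting in which nobody dies. Neither curve is the duration of symptom relief that 10.1 says is measured. Section 4 says a randomised dose-escalation study may follow from these results, so it should be clear what the durability figure means.

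**Working it through.** **The plan's own figure.** The Protocol gives no number for the progression endpoint. Its only calculation is the primary sample size, which reproduces if the 70% in Section 16.1 is read as the feasible proportion: n = [(1.96 × √(0.9 × 0.1) + 0.842 × √(0.7 × 0.3)) / 0.2]² = 23.70, rounded up to 24. Then 24/0.70 = 34.3, stated as 34. Nothing below changes it.

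**Inputs.** Median survival M_d = 3 to 12 months (Section 6) and a six-month horizon (last protocol visit). The Protocol gives no symptom-progression rate, so the median time to symptom progression M_p is assumed to be 3 to 24 months. Hazards are assumed constant and independent: h_d = ln 2/M_d and h_p = ln 2/M_p.

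**Step 1: deaths by six months**, 1 − exp(−6h_d):

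| Median survival (months) | Dead by 6 months |
|---|---|
| 3 | 75% |
| 6 | 50% |
| 9 | 37% |
| 12 | 29% |

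Of 34 patients this is about 10 (0.293 × 34) to 26 (0.75 × 34 = 25.5).

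**Step 2: death counted as an event.** The share of first events that are deaths is h_d/(h_d + h_p) = M_p/(M_p + M_d):

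| M_d \ M_p | 3 | 6 | 12 | 18 | 24 |
|---|---|---|---|---|---|
| 3 | 50% | 67% | 80% | 86% | 89% |
| 6 | 33% | 50% | 67% | 75% | 80% |
| 9 | 25% | 40% | 57% | 67% | 73% |
| 12 | 20% | 33% | 50% | 60% | 67% |

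Deaths are the majority only when symptom progression is slower than death.

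**Step 3: death censored.** One minus Kaplan-Meier tends to 1 − exp(−6h_p). The proportion who actually progress before dying is h_p/(h_p + h_d) × [1 − exp(−6(h_p + h_d))]. With an assumed 30% six-month risk in the absence of death, h_p = −ln(0.7)/6 = 0.0594 per month:

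| Median survival (months) | One minus Kaplan-Meier | Cumulative incidence | Overstatement | Deaths as share of composite events |
|---|---|---|---|---|
| 3 | 30% | 16.9% | 13 points | 80% |
| 6 | 30% | 22.1% | 8 points | 66% |
| 12 | 30% | 25.6% | 4 points | 49% |

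Over the Step 2 grid the overstatement runs from about 2 points (M_d 12, M_p 24: 15.9% against 13.5%) to 28 points (both 3: 75.0% against 46.9%). At M_d = M_p = 6 it is 50.0% against 37.5%.

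**Step 4: one cohort, two curves.** At median survival 6 months and the 30% risk, 0.70 × 0.50 = 35% are alive without symptom progression at six months, 22% have progressed first, and the remaining 43% have died first. A Kaplan-Meier curve stands at 35% if death is an event and at 70% if death is censored. The wording of 16.3 does not say which would be reported.

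**The case against.** - **Kaplan-Meier is a proper estimator for composite PFS, and by usual meaning PFS includes death.** This stands. The method is not wrong in itself, and no passage says that deaths are censored. The fault is that the event and the role of death are not fixed, and that the result is equated with duration of relief.
- **Competing-risk handling and censoring rules commonly sit in an SAP, which is not shown.** This is true of the detail. It does not dispose of the conflict between the synopsis, Sections 4, 10.1, 14 and 16.3 and the flowchart, which is in the Protocol and which an SAP would inherit.
- **A reader might infer that the curve will mostly reflect death.** The documents do not support that. It needs death to be an event, which is not stated, and symptom progression to be slower than death, for which no rate is given. The share ranges from 20% to 89%. Nor do the documents support calling these deaths unrelated to local control.
- **A cumulative incidence curve is not a duration either, and it falls when more patients die early.** This is correct, and it limits how the added curve may be described.
- **The effect is small beside sampling error.** Around 30%, the 95% half-width is 1.96 × √(0.3 × 0.7/n), or 18 points at n = 24 and 15 points at n = 34. The central 8-point gap lies within that. But it is a systematic error in one direction, and the choice between the two curves in Step 4 moves the figure by 35 points.
- **Overall survival and VAS are separate secondary endpoints.** This softens the consequence, since survival and symptom course can be looked at apart from PFS. It does not tell the reader what the reported PFS means.

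**Conclusion.** The point holds as a contradiction in a secondary endpoint with a real effect on interpretation. The progression endpoint has several names and scopes, death has no stated role, and the one method offered is not tied to the symptom endpoint of 10.1. With 29% to 75% of patients expected to die by six months, a single PFS curve cannot be read as duration of symptom relief. With death as an event it may largely reflect death; with death censored it overstates symptom progression, by 8 points in the central case.

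These sizes rest on constant, independent hazards, on the eligibility range standing for the cohort's median survival, and on assumed symptom-progression rates. The direction of each effect does not depend on the particular rates chosen. The conclusion does not extend to Kaplan-Meier being an invalid choice, nor to the primary endpoint or the sample size.

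**What to change.** 1. Use one definition of the symptom-based endpoint (LPFS) in the synopsis, Sections 4, 10.1, 14 and 16.3 and the Appendix 4 flowchart. State what counts as progression of the dominant symptom. If general PFS is also meant, as Section 4 suggests, define it separately.
2. State that death counts as an event in LPFS. Keep Kaplan-Meier for it and describe the result as time alive without symptom progression.
3. Add an Aalen-Johansen cumulative incidence curve for dominant-symptom progression with death as a competing event. Report it as the probability of symptom progression before death, not as a duration.
4. Reconcile Section 14 with this definition: the committee's listed material does not include the VAS on which a symptom endpoint depends. Section 17.2, under which disease progression ends participation, must also be reconciled with collecting symptom data to six months.

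The cost is wording plus one extra analysis. VAS and survival are already scheduled at the end of radiotherapy and at 1, 3 and 6 months, so no new assessment is needed, although the committee would have to be sent symptom data already recorded.
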